1.8 Clinical Trial Experience Using the Intravenous Formulation of Ixazomib

See the IB for descriptions of the 2 studies that investigated IV ixazomib in advanced solid tumors and advanced lymphoma (Studies C16001 and C16002, respectively).

1.9 Study Rationale

One of the major challenges in the current era of organ transplantation is to find suitable organs for highly sensitized patients. These patients have developed antibodies against major histocompatibility (HLA) antigens due to previous transplantation, blood transfusion, or pregnancy. Despite some success, current desensitization protocols are limited because of their complexity and inability to reduce donor specific antibodies (DSA) in 30-90% of patients, and the absence of effective agents against plasma cells, which actually produce the HLA alloantibodies. As a result, many patients die on dialysis prior to receiving a transplant.

Our long-term goal is to improve the quality-of-life and survival of kidney transplant recipients. Our specific hypothesis for this proposal is that ixazomib (Ninlaro[®]) can significantly reduce DSA production and allow for kidney transplantation in highly sensitized patients. Ixazomib is a second generation proteasome inhibitor, recently approved by the FDA for the treatment of multiple myeloma. We further hypothesize that specific molecular and cellular indices can be predictive of treatment response and toxicity. These hypotheses are based on preliminary findings demonstrating that: (a) The first-generation proteasome inhibitor, bortezomib (Velcade[®]), is an effective option for the treatment and prevention of antibody mediated rejection (AMR) in clinical settings; (b) Ixazomib prevents acute AMR in a robust preclinical model of kidney transplantation by downregulating B cell activation, antigen presentation, T cell and B cell signaling, and microcirculation inflammation; (c) IgG subclasses, IgG complement binding capacity, and serum B cell activating factor (BAFF) and APRIL (a proliferation-inducing ligand) are associated with AMR and graft loss in kidney transplantation.

Based on these observations and the critical need to define effective desensitization strategies, we propose a pilot exploratory, proof of concept, open-label, single-center phase II clinical trial entitled **IXAzomib for DESensitization (IXADES)**. We will examine the safety and efficacy of ixazomib for desensitization of highly sensitized kidney transplant candidates and conduct mechanistic studies to address the role of IgG subclasses, IgG complement binding capacity, non-HLA antibodies, T and B cell phenotypes, and BAFF/APRIL in immune monitoring and regulation.

Sensitization in kidney transplant candidates. Alloantibodies (anti-HLA antibodies) arise through previous transplants, blood transfusions, and pregnancy. Currently, 39% of patients on the active kidney transplant waitlist are sensitized, evidenced by a Panel Reactive Antibody (PRA) $\geq 1\%$ (33). Of these, nearly 15,000 are highly sensitized, which means that they have a PRA $\geq 80\%$ (33). Transplant rates vary by PRA, ranging from 143.0 per 100 active waitlist years for candidates with a PRA of less than 1% to only 6.9 for those with a PRA of 98% or higher (33). Median waiting time for kidney transplantation in highly sensitized patients approaches 12 years, which is more than 3 times than for non-sensitized patients (33). As a result, a significant number of highly sensitized patients die before receiving a transplant, outlining the critical importance of desensitization strategies.

Desensitization protocols. The two approaches for helping highly sensitized patients are: 1) To increase the chance of finding a crossmatch negative donor, or 2) To remove the pre-existing antibodies using desensitization protocols (7-11). Emerging evidence suggests that strategies to improve transplant rates in highly sensitized patients enhance survival rates and the quality of life, while reducing costs compared to chronic dialysis (12, 13). Current desensitization protocols combine Rituximab (anti-CD20 monoclonal antibody) to deplete B cells, and plasmapheresis plus intravenous immunoglobulins (IVIG) to block or remove preformed DSA (7-11). Since no agent previously used in transplantation has the adequate ability to inhibit mature plasma cells, there has been no effective way of reducing or preventing antibody production besides targeting B cells. Therefore, despite some success, contemporary desensitization protocols are limited by their inability to desensitize 30 to 90% of patients (5, 8, 14). For example, using a preconditioning regimen similar to the one used at our institution combining plasmapheresis, IVIG and Rituximab, the Mayo Clinic Transplant Program was unable to desensitize 15/29 patients who had an CDC crossmatch titer $\geq 1:8$ (8). Similarly, Marfo et al demonstrated that pretransplant desensitization with high dose IVIG and rituximab was not successful in sensitized kidney transplant candidates with cPRA levels higher than 90% (5). It is for this reason that we propose a pilot desensitization study targeting the cells responsible for generating alloantibodies using ixazomib, a recently approved therapy for multiple myeloma.

Ixazomib (Ninlaro®, Takeda-Millennium Pharmaceuticals, Inc). In kidney transplantation, the first generation proteasome inhibitor bortezomib (Velcade®) has been utilized as part of desensitization (16) and AMR treatment strategies (14, 34-37). Ixazomib is a second generation **oral** proteasome inhibitor, recently approved for the treatment of multiple myeloma (38-43). Ixazomib is administered as a citrate ester, ixazomib citrate, that rapidly hydrolyzes under physiological conditions to its biologically active form, ixazomib. The active form potently, reversibly and selectively inhibits the proteasome (39-41). It is **more effective** than earlier generation proteasome inhibitors in targeting plasma cells **with improved side effect** profile (38, 44-49). Having a more potent, less toxic proteasome inhibitor that does not need to be delivered intravenously and can be used in patients with reduced kidney function will be clinically advantageous (46). Despite the absence of data on the use of ixazomib in clinical transplantation (only FDA approved in November 2015), we have been the only group to demonstrate that the drug is safe and effective for the treatment of antibody mediated rejection (AMR) in a robust preclinical model (19). More specifically, it is unknown whether ixazomib depletes plasma cells, prevents their generation or both. For example, the effects of treatment on differentiated bone marrow-derived CD138⁺ **plasma cells** in clinical transplantation are unknown. These antibody producing cells thrive in a microenvironment rich in BAFF and APRIL generated by stromal mesenchymal stem cells (MSCs). We propose to test the safety and efficacy of this drug in a phase II trial for desensitization.

BAFF/APRIL and Desensitization. BAFF and APRIL are homologues and members of the tumor

necrosis factor superfamily (50). They are produced by neutrophils, macrophages, dendritic cells and stromal mesenchymal stem cells in the bone marrow (1, 50, 51). Both cytokines are potent activators and survival factors for B cells and plasma cells. Through their receptors BAFF-R (BAFF receptor), TACI (transmembrane activator and calcium modulator and cyclophilin ligand interactor) and BCMA (B cell maturation protein), BAFF/APRIL activate the prosurvival NF-kappaB and MEK signaling pathways (1, 50, 51). In animal models, excess BAFF leads to the development of autoimmune disorders including lupus nephritis, while APRIL deficient mice lack proper activation and maturation of plasmablasts (50, 51). High levels of BAFF/APRIL are detected in the serum of patients with autoimmune disease, which in some studies correlate with disease activity (50, 51). BAFF and APRIL inhibitors such as Belimumab (Lymphostat-B) and TACI-Fc fusion protein (Atacicept) have been recently used in phase II and III clinical trials of lupus and rheumatoid arthritis (50, 51). Consistent with these data, serum BAFF levels are increased in kidney transplant recipients undergoing AMR, where this cytokine may play an important role in the immune response to the allograft (1, 52). We hypothesize that in highly sensitized patients, BAFF/APRIL generated by bone marrow-derived mesenchymal stem cells (BM-MSCs) play a key role in the survival and maturation of donor-specific plasma cells and that serum BAFF/APRIL levels have an important clinical value in predicting and monitoring treatment response.

Immunoglobulins and Desensitization. Terasaki et al. identified HLA antibodies in the serum of patients after transplantation nearly 45 years ago (53). Preexisting (54-56) and de novo circulating antibodies (dnDSA) (57, 58) have been shown to compromise renal allograft survival. These antibodies may be directed against HLA or non-HLA molecules on endothelial cells including angiotensin II type 1 receptor (AT1R), or endothelin type A receptor (ETAR) (59-61). It is important to note that currently available HLA antibody tests are qualitative and have not been cleared by the FDA for quantitative measurements (62). In addition, *the critical issue for patient care is discerning which of the detected antibodies are pathogenic as many patients with donor specific antibodies prior and after transplantation have stable allograft function and experience no rejection.*

For example, patients with dnDSA at the time of biopsy have worse graft survival than those with preexisting DSA, indicating a more pathogenic role for dnDSA (63). Similarly, it has been proposed that the assessment of the complement-binding capacity of donor-specific anti-HLA antibodies by the C1q assay may be useful in identifying patients at high risk for kidney-allograft loss (64). However, we have recently conducted studies demonstrating that the C1q binding activity by DSA largely reflects differences in antibody strength, questioning the biologic significance of this test (65). It has also been proposed that among IgG subclasses, IgG3 may have a more pathogenic role in AMR (66, 67) but the role of immunoglobulin subclasses in desensitization and kidney transplantation remains unknown. To address these questions, we propose to identify risk stratification strategies and to determine the pathogenic role and specificity of anti-HLA, non-HLA-DSA and complement fixing antibodies in desensitization.

Future Biomedical Research. Subjects will be asked in the consent form if they agree to allow a portion of their bone marrow aspiration sample to be used for a future research project that will involve growing the mesenchymal stromal cells in [name] laboratory. If subjects do not achieve desensitization during their participation in this research study, they may be offered injection with their mesenchymal stromal cells, in an effort to achieve desensitization in a future research study.

1.10 Potential Risks and Benefits

Please refer to the current ixazomib IB and SMA for a complete list of the risks of ixazomib. The clinical benefit of ixazomib continues to be studied in a comprehensive and global development plan that involves studies sponsored by Millennium. Ixazomib appears to show a significant impact on the production of allo antibodies in preclinical studies of AMR. The preliminary findings are favorable when considering historical and currently available therapies for the patient populations evaluated. Though additional data are needed to characterize the clinical benefit of this drug, the emerging data supports expanded development of ixazomib for the treatment of patients with advanced malignancy.

This study will be conducted in compliance with the protocol, good clinical practice (GCP), applicable regulatory requirements, and International Conference on Harmonisation (ICH) guidelines.

Compliance with eligibility criteria: The PI will sign-off on the eligibility checklist for each subject prior to study drug dispensation.

The risks to subjects in this trial will be minimized by compliance with eligibility criteria, clinical monitoring, adherence to protocol contraception requirements and investigator guidance regarding specific safety areas.

The specific safety areas that will be closely monitored in this subject population are;

Ixazomib: thrombocytopenia, diarrhea, fatigue, nausea, vomiting, rash, risk of reactivation of herpes infection, neutropenia, fluid deficit, hypotension, posterior reversible encephalopathy syndrome (PRES), and transverse myelitis.

Bone Marrow Aspiration Risks: This procedure may be very painful; however, the pain only lasts for about 15 to 30 seconds. The hip area may be sore for a day or two. It is possible, but not likely that the subject could get an infection or have a large amount of bleeding. In very rare cases, people might have an allergic reaction to the local anesthesia. The allergic reaction could include rash/hives, flushing of the face, itching, wheezing and tightness in the throat.

For subjects that are on warfarin, INR levels will be checked prior to the BMA, and pressure will be applied for

- 10 minutes after the procedure if INR 1.5-2
- 15 minutes after the procedure if INR 2-2.5
- 20 minutes after the procedure if INR > 2.5

Warfarin dosing will not be adjusted. Blood Draw Risks: The risks of taking blood include pain, a bruise at the point where the blood is taken, redness and swelling of the vein and infection, and a rare risk of fainting.

Overall, the balance of benefit and risk supports the proposed clinical study to evaluate the potential of ixazomib to significantly reduce DSA production and allow for kidney transplantation in highly sensitized patients.

Subject Remuneration

Subjects will receive \$100 after Visit 1 and will receive \$20 per visit for visits 2 - 13. Payment will be made by check approximately 6 weeks after each study visit.

2. STUDY OBJECTIVES

2.1 Primary Objectives

Specific Aim 1. To determine the safety and efficacy of ixazomib as a desensitization strategy. 10 highly sensitized kidney transplant candidates on the waitlist for more than 24 months will receive ixazomib 3 mg (and dexamethasone 20 mg) on days 1, 8, and 15 of a 28 cycle for 12 months. The primary objective is to evaluate the safety (distal neuropathy, thrombocytopenia, and gastrointestinal symptoms) and efficacy (decline in cPRA > 20%) of ixazomib. The secondary efficacy endpoint is transplantation rate within 12 months of therapy.

2.2 Secondary Objectives

Specific Aim 2. Identify immune indices which predict the course of disease and/or response to treatment in highly sensitized patients. Mechanistic studies will use bone marrow and blood obtained from subjects in Aim 1 to determine the effect of treatment on immune regulation and reconstitution after therapy. Since the bone marrow microenvironment produces BAFF/APRIL and supports plasma cell maturation, we will determine the effect of therapy on the generation of BAFF/APRIL by bone marrow mesenchymal stem cells and the survival of bone marrow-derived plasma cells after desensitization. We specifically propose to:

- Identify if bone marrow plasma cells, IgG subsets, and circulating BAFF/APRIL predict outcomes.
- Determine if treatment is effective in downregulating circulating BAFF/APRIL and anti-HLA, endothelin-1 type A receptor (ETAR), angiotensin type 1 receptor (AT1R), and complement fixing C1q antibodies.
- Identify immunological indices which predict treatment toxicity and responders vs. non-responders.

In summary, sensitization is a significant clinical and immunological problem in kidney transplantation. In a unique effort involving the University of Wisconsin's Divisions of Nephrology, Transplantation, and Hematology-Oncology (clinical core), The University of Michigan (Plasma cell core), and The Terasaki Foundation Laboratory (DSA core), coordinated by the UW Office of Clinical Trials, an experienced clinical research organization, we propose the planning of a pilot phase II safety and efficacy trial of ixazomib for desensitization of highly sensitized kidney transplant candidates. We further outline mechanistic studies to determine the pathogenesis of alloantibody generation and define novel biomarkers and surrogate endpoints for a future Clinical Trial Implementation grant (NIAID PAR-13-149). The results are expected to have a positive impact as proposed studies are crucial steps towards developing improved therapies and monitoring options to reduce the long-term impact of sensitization.

3. STUDY ENDPOINTS

3.1 Primary Endpoints (safety and efficacy)

Primary efficacy and safety endpoint:

- Efficacy endpoint: A decline in cPRA > 20%.
- Safety endpoint: infections, malignancies, hematological complications including leucopenia, anemia, and thrombocytopenia, cardiovascular complications and events, distal neuropathy, gastrointestinal symptoms, and immunosuppression-related adverse effects.

3.2 Secondary Endpoints (efficacy endpoint)

Secondary efficacy endpoint: Successful transplantation in 12 months

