Specific Aim 1. To determine the safety and efficacy of ixazomib as a desensitization strategy. There is currently no effective desensitization strategy for highly sensitized patients defined as calculated Panel of Reactive Antibodies (cPRA) $\geq 80\%$. For this study, 10 highly sensitized kidney transplant candidates on the waitlist for more than 24 months will receive ixazomib 3 mg (and dexamethasone 20 mg) on days 1, 8, and 15 of a 28 cycle for 12 months. The primary objective is to evaluate the safety (distal neuropathy, thrombocytopenia, and gastrointestinal symptoms) and efficacy (decline in cPRA $> 20\%$) of ixazomib. The secondary efficacy endpoint is transplantation rate within 12 months of therapy.

Specific Aim 2. Identify immune indices which predict the course of disease and/or response to treatment in highly sensitized patients. Mechanistic studies will use bone marrow and blood obtained from subjects in Aim 1 to determine the effect of treatment on immune regulation and reconstitution after therapy. Since the bone marrow microenvironment produces BAFF/APRIL and supports plasma cell maturation, we will determine the effect of therapy on the generation of BAFF/APRIL by bone marrow mesenchymal stem cells and the survival of bone marrow-derived plasma cells after desensitization. We specifically propose to:

- Identify if bone marrow plasma cells, IgG subsets, and levels including free light chains, and circulating BAFF/APRIL predict outcomes.
- Determine if treatment is effective in downregulating circulating BAFF/APRIL and anti-HLA, endothelin-1 type A receptor (ETAR), angiotensin type 1 receptor (AT1R), and complement fixing C1q antibodies.

Figure 1. Protocol Summary

| |
|--|
| Study Title: IXAzomib for DESensitization (IXADES) |
| Phase: II |
| Number of Patients: 10 |
| Study Objectives The primary objective is to evaluate the efficacy of ixazomib in desensitizing highly sensitized kidney transplant recipient, defined as a decline in calculated PRA (cPRA) > 20%, or successful transplantation within 12 months. The secondary objective is to determine the toxicity and tolerability of ixazomib with particular focus on distal neuropathy, thrombocytopenia, and gastrointestinal symptoms. |

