Our long-term goal is to improve the quality-of-life and survival of kidney transplant recipients. Our specific hypothesis for this proposal is that ixazomib can significantly reduce DSA production and allow for kidney transplantation in highly sensitized patients. Ixazomib is a second generation proteasome inhibitor, recently approved by the FDA for the treatment of multiple myeloma. We further hypothesize that specific molecular and cellular indices can be predictive of treatment response and toxicity. These hypotheses are based on preliminary findings demonstrating that: (a) The first-generation proteasome inhibitor, bortezomib (Velcade®), is an effective option for the treatment and prevention of antibody mediated rejection (AMR) in clinical settings; (b) Ixazomib prevents acute AMR in a robust preclinical model of kidney transplantation by downregulating B cell activation, antigen presentation, T cell and B cell signaling, and microcirculation inflammation; (c) IgG subclasses, IgG complement binding capacity, and serum B cell activating factor (BAFF) and APRIL (a proliferation-inducing ligand) are associated with AMR and graft loss in kidney transplantation.

Based on these observations and the critical need to define effective desensitization strategies, we propose a pilot exploratory, proof of concept, open-label, single-center phase II clinical trial entitled **IXAzomib for DESensitization (IXADES)**. We will examine the safety and efficacy of ixazomib for desensitization of highly sensitized kidney transplant candidates and conduct mechanistic studies to address the role of IgG subclasses, IgG complement binding capacity, non-HLA antibodies, T and B cell phenotypes, and BAFF/APRIL in immune monitoring and regulation.

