Duration of Treatment and Follow-up. All participants, those that receive a kidney transplant during the defined period and those that do not will be followed for the entire length of treatment, plus one month following the last dose of the study drug. All subjects will be asked to return for a final study visit approximately one month following the last dose of study drug. During this final study visit, subjects will undergo physical examination, bone marrow aspirate collection, CBC, LFT check, ECG and echocardiogram.

Bone Marrow Aspirate Collection Procedure: Subjects will be given the option of having the bone marrow aspirate performed under conscious sedation or local anesthetic only. The bone marrow aspirate will be collected in a transplant clinic room. If the bone marrow aspiration is done under conscious sedation, subjects will be given instructions to fast for six hours before the procedure (medications are allowed) and not to drive themselves home or operate dangerous equipment after the procedure.

Measurement of effect. We will determine the effect of ixazomib by measuring cPRA, whether patients receive a kidney transplant while participating in the study, antibody strength by MFI, and the toxicity (measured by the incidence of adverse events) of the treatment quarterly up to the end of the study.

Ixazomib Administration

All protocol-specific criteria for administration of study drug must be met and documented before drug administration. Study drug will be dispensed only to eligible patients by a member of the study team. Patients should be monitored for toxicity, as necessary, and doses of ixazomib should be modified as needed to accommodate patient tolerance to treatment; this may include symptomatic treatment, dose interruptions, and adjustments of ixazomib dose (see Section 6.3).

Capsules of ixazomib will also be referred to as study drug. Study drug will be supplied by Millennium as capsules 0.5, 2.3, and 3.0 mg ixazomib. The prescribed administration of ixazomib doses in this study is 9 mg ixazomib in a 28 day cycle. Patients should be instructed to swallow ixazomib capsules whole, with water, and not to break, chew, or open the capsules. Ixazomib should be taken on an empty stomach (no food or drink) at least 1 hour before or at least 2 hours after food. Each capsule should be swallowed separately with a sip of water. A total of approximately 8 ounces (240 mL) of water should be taken with the capsules.

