7. STATISTICAL AND QUANTITATIVE ANALYSES

7.1 Statistical Methods

More than 50% of patients with CDC T cell crossmatch titers $\geq 1:8$ and/or cPRA $> 80\%$ fail to respond to desensitization (5, 8). In this pilot exploratory, proof of concept, open-label, single-center phase II clinical trial, we hypothesize that our study will have a higher rate of transplantation. [name], PhD, epidemiologist and biostatistician in the division of nephrology, will perform the statistical analyses. *Primary* efficacy (decline in cPRA $> 20\%$) and safety (discontinuation of therapy due to adverse events) endpoint will be analyzed using the exact binomial test. The *secondary* endpoint (time to transplantation) will be assessed using Kaplan-Meier analyses and log rank tests. Baseline characteristics will be compared between participants with and without the primary end point using the 2-sample t test for continuous variables and the Fisher's exact test for categorical variables. Relationships between serum BAFF/APRIL, antibodies, and baseline cPRA will be assessed using the Pearson correlation coefficient. The influence of serum BAFF/APRIL, antibodies, and bone marrow plasma cells on end points of interest will be investigated using Kaplan-Meier curves and Cox proportional-hazards models.

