7.1.6 Efficacy Analysis

Primary outcome will be a decline in cPRA > 20%. Secondary outcome will be kidney transplantation within 12 months of therapy. These outcomes will be assessed using paired t-Test, Kaplan-Meier methods and log rank tests, where appropriate. In addition, we will analyze the change in HLA antibody strength by comparing the MFI values pre and post therapy.

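### The secondary endpoint counts every transplant within 12 months and sets no reference rate, so one or two transplants among 10 patients cannot by themselves be attributed to treatment

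*Combined protocol and SAP*

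**What the plan says.** The hypothesis in section 1.1.1 is causal: "ixazomib can significantly reduce DSA production and allow for kidney transplantation in highly sensitized patients". The endpoint that carries the transplant half of it has no attribution condition. Section 3.2 reads "Secondary efficacy endpoint: Successful transplantation in 12 months" and section 7.1.6 reads "Secondary outcome will be kidney transplantation within 12 months of therapy". Neither they nor the statements in the Protocol Summary and section 2.1 mention donor type, donor HLA, crossmatch against baseline serum, or a prior fall in antibody. Section 6.2 says the effect of ixazomib will be determined from several measures, one of which is "whether patients receive a kidney transplant while participating in the study". The others are cPRA, antibody strength by MFI, and adverse events.

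On analysis, section 7.1 says the secondary "endpoint (time to transplantation) will be assessed using Kaplan-Meier analyses and log rank tests". It expects a higher transplant rate but gives no numerical reference and no groups for the log rank test. The trial is open-label and single-arm, with 10 patients (sections 4.2 and 7.1.2).

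On background, section 1.9 reports transplant rates per 100 active waitlist years that run from 143.0 at PRA below 1% "to only 6.9 for those with a PRA of 98% or higher", and a median wait approaching 12 years for highly sensitized patients. Entry requires cPRA of at least 80% and more than 24 months of active listing (section 5.1).

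**The concern.** A transplant supports desensitization most directly when the donor was out of reach because of antibody present before treatment. The endpoint makes no such distinction. A patient who takes an offer that was already acceptable on Day 1, with antibody unchanged, is scored the same as one whose antibody fell and opened up a new donor. A randomized control arm would absorb the background transplants, but this trial has none.

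With 10 patients, one or two such transplants would make up a visible share of the result and could be reported as support for the hypothesis. They also feed the biomarker aim: section 3.3 compares baseline BAFF/APRIL according to whether patients reached the primary or secondary endpoints, so a background transplant would be analysed there as a response.

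A smaller related issue is that Kaplan-Meier treats death as censoring. Section 1.9 says "As a result, many patients die on dialysis prior to receiving a transplant", so death before transplant is a foreseeable outcome in this population.

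**Working it through.** **The plan's own figures.** Section 7.1.1 gives figures for the cPRA endpoint only. The exact 95% interval for 3/10 recomputes to 6.7%-65.2%, as stated. The chance of at least one success in 10 at a true rate of 0.2 is 1 - 0.8^10 = 89.3%, consistent with the stated figure of more than 80%. No corresponding figure is given for transplantation, so there is none to reproduce.

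**Inputs.** n = 10 (section 4.2). Background rate r = 0.069 per patient-year at PRA 98% or higher (section 1.9). Follow-up is taken as T = 1 year. Assumptions: constant hazard, continuous active listing, no deaths or withdrawals.

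**Per-patient probability with no drug effect.** p = 1 - exp(-0.069) = 0.0667, so the expected count is 10 x 0.0667 = 0.67.

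**Binomial counts** (each patient transplanted at most once):
- P(0) = exp(-0.69) = 0.5016, so P(at least 1) = 0.498
- P(1) = 10 x 0.0667 x exp(-0.621) = 0.358, so P(at least 2) = 0.140
- P(2) = 45 x 0.0667^2 x exp(-0.552) = 0.115, so P(at least 3) = 0.025

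A Poisson count with mean 0.69 gives 0.498, 1 - 0.5016 x 1.69 = 0.152, and 1 - 0.5016 x (1 + 0.69 + 0.238) = 0.033. The binomial fits better because nobody is counted twice.

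**Sensitivity to follow-up.** Using 336 days (12 cycles of 28 days), the binomial values are 47.0%, 12.3% and 2.0%. Using 373 days (the final visit), they are 50.6%, 14.5% and 2.6%.

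**Cross-check from the median wait.** A 12-year median implies r = ln 2 / 12 = 0.0578 and p = 0.0561. P(at least 1) is then 1 - 2^(-10/12) = 43.9%, P(at least 2) = 10.5% and P(at least 3) = 1.6%.

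**Rates the documents do not give.** No rate is stated for cPRA 80-97%. The range below is an assumption, shown only for sensitivity:

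| Assumed rate per 100 years | P(at least 1) | P(at least 2) | P(at least 3) |
|---|---|---|---|
| 10 | 63% | 25% | 6% |
| 15 | 78% | 42% | 15% |
| 20 | 86% | 57% | 27% |

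**Time to transplant.** As an invented illustration, suppose 3 of 10 patients die or are delisted, and two of the remaining seven are then transplanted. Censoring the three gives 1 - KM = 1 - (6/7)(5/6) = 28.6%. Cumulative incidence with those events as competing risks is 2/10 = 20%. The contrast applies only to death or delisting. If the three had merely left the study, for reasons unrelated to their chance of transplant, censoring would be proper and 28.6% the appropriate estimate.

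**The case against.** The waitlist criterion in section 5.1 is the best answer in the documents. Patients must have waited more than 24 months, expressly to establish that sensitization prevents a deceased donor transplant. That removes those who receive early compatible offers, so the true background may lie below 6.9 per 100. This stands as a reason to treat that figure as approximate. It does not make the background zero: the criterion does not address living donors, and section 1.9 reports transplants even at PRA 98% or higher.

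It is also fair that transplantation is an objective outcome that matters to patients, that the trial is an exploratory pilot with no decision rule on the transplant count, and that transplant is not read alone. cPRA and DSA are measured five times, MFI is compared before and after therapy, and in 10 patients a transplant without antibody decline would be visible in the listings. All of this stands, and it is why the endpoint should be kept. It does not supply a pre-specified rule for saying which transplants support the hypothesis.

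Two stronger readings do not hold. A reader might infer that the endpoint can show nothing about the drug. However, three or more transplants would have only about a 2.5% chance at 6.9 per 100, so a high count would be indirect evidence if that benchmark applied. A reader might also infer from the Protocol Summary, whose primary objective adds "or successful transplantation within 12 months", that one background transplant would meet the primary test. Sections 3.1 and 7.1.1 define and test the primary outcome on cPRA decline alone.

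**Conclusion.** The point holds in a limited form. With no control arm, no reference rate and no attribution rule, one or two transplants among 10 patients cannot by themselves be attributed to treatment. At the protocol's own rate the chance with no drug effect is about 50% for at least one and 14-15% for at least two. These figures assume a constant hazard, a full year of active listing, and that the rate for PRA 98% or higher applies to this cohort. The cohort enters at cPRA 80% or higher and has already waited two years. The documents do not allow the size or net direction of those departures to be fixed.

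Three or more transplants would be harder to explain as background at 6.9 per 100. Even then no single transplant could be attributed, and the inference weakens if the rate at cPRA 80-97% is materially higher.

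The Kaplan-Meier point is secondary. It concerns death and delisting only, and the documents give no 12-month death rate from which to size it. The primary endpoint and the sample size are unaffected.

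**What to change.** Keep the all-transplant endpoint and add the following to the SAP and CRF.

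1. Report all transplants as x/10 with an exact 95% CI, beside an expected background count. Fix the reference rate and its source in advance, matched to cPRA where possible, and apply it to each patient's active listing time.
2. As a supportive analysis, class each transplant as *incompatible at baseline* (the donor carries at least one HLA antigen with Day 1 antibody above a cut-off fixed in the SAP) or *already compatible at baseline*.
3. For the first class, report whether that antibody fell before transplant, using the last pre-transplant sample. With quarterly sampling this may be up to about three months old. Without this step, a transplant across persisting antibody would count as support.
4. Record donor HLA typing and donor type on the CRF. Neither is a listed study item now, and no antibody cut-off is stated.
5. Base any statement that treatment enabled transplantation on the incompatible-at-baseline group with a documented antibody fall. State that ixazomib cannot be separated from dexamethasone.
6. For time to transplant, use cumulative incidence with death or delisting as competing events. Patients who only leave the study stay censored or are followed for transplant status. Either name the groups for the log rank test or drop it.

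The cost is SAP and CRF wording and one HLA comparison per transplant, with no change to treatment, visits or sample size. Fewer transplants may count as support. Section 1.9 describes HLA antibody tests as qualitative, so assay variation near the cut-off may misclassify some, and natural fluctuation may pass for a fall. The class is therefore supportive evidence and does not replace a control.
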